6.8. Other Safety Assessments

6.8.1. Best-Corrected Visual Acuity

Best-corrected visual acuity (BCVA) measurement will be performed in each eye at all study visits with the logMAR eye chart using the subject's best corrective lens prescription eyeglasses or trial frame lenses, if applicable. The subject's BCVA must be determined (via refraction) if corrected or uncorrected visual acuity is not logMAR 0.0 (equivalent to 20/20). This refraction must be used for all VA assessments for the duration of the study. The subject must wear the same glasses/trial frame, if applicable, at each visit. Ambient room lighting should be consistent for a given subject throughout the study period. Consult the Study Reference Manual for specific details regarding the evaluation procedures.

6.8.2. Biomicroscopy and External Eye Exam

A slit-lamp examination will be conducted at each study visit to assess the anterior ocular structures, including lid, cornea, conjunctiva, anterior chamber, iris, lens, and posterior capsule (if pseudophakic). Abnormalities will be documented. Consult the Study Reference Manual for specific details regarding the evaluation procedures.

6.8.3. Dilated Fundus Exam

A fundus exam consisting of the vitreous, optic nerve, macula, and peripheral retina will be conducted, and the structures will be graded as normal or abnormal. Consult the Study Reference Manual for specific details regarding the evaluation procedures.

6.8.4. Intraocular Pressure Measurement

Intraocular pressure will be measured utilizing a Goldmann tonometer. If possible, the same observer should perform the assessment and the same calibrated instrument should be used for a given subject throughout the study. To avoid IOP changes due to the diurnal rhythm, the

IOP measurements should be performed at approximately the same time of the day each time. Consult the Study Reference Manual for specific details regarding the evaluation procedures.

6.8.5. Investigational Product Comfort Assessment

Subjects will rate the comfort of IP instillation according to the following 4-point scale:

- 0 = No discomfort
- 1 = Mild discomfort
- 2 = Moderate discomfort
- 3 = Severe discomfort

6.9. Screen Failures

A screen failure is a subject who has given informed consent and failed to meet the inclusion criteria or met at least 1 of the exclusion criteria, and has not been randomized into the study. Based on Investigator discretion and Sponsor approval, subjects who initially failed to meet the inclusion/exclusion criteria may be rescreened at a later time if their eligibility status has changed. The subject will retain the same subject identification number that he/she was assigned at the first screening.

6.10. Subject Withdrawal Criteria

The following are the criteria for considering withdrawal from the study:

- Withdrawal of subject consent. The subject may request for any reason at any time to be withdrawn from the study.
- The Sponsor terminates the study.

If a subject withdraws from the study, the reason for withdrawal will be recorded in the eCRF.

If a study subject fails to attend a study visit at any point during the study period, every effort should be made to keep the subject in the study and conduct all study visits as scheduled; all attempts to contact the subject must be documented. If the subject relocates during the study period, the CRO should be contacted to determine if there is a possibility that the subject could continue at another clinical site.

6.11. Appropriateness of Measurements

The efficacy and safety assessments in this study are standard for ophthalmologic investigations, and their reliability, accuracy, and relevance is well established. Collection of AEs to monitor drug safety is standard in clinical studies.

7. STUDY ACTIVITIES

Table 1 provides a tabular summary of all scheduled visits and procedures to be performed during the clinical study.

7.1. Visit 1 (Day -14 ± 2/Screening Visit)

Procedures performed at Screening, Visit 1/Day -14 ± 2 will include the following:

- Obtain written informed consent
- Inclusion/exclusion criteria
- Demographics
- Medical and ocular history
- Concomitant medication review
- Urine pregnancy test (women of childbearing potential only)
- SANDE
- BCVA (logMAR)
- Biomicroscopy/external eye exam
- TBUT
- Corneal fluorescein staining
- Conjunctival lissamine green staining
- Anesthetized Schirmer's test
- IOP measurement
- Dilated fundus exam
- Re-review inclusion/exclusion criteria
- Dispense run-in medication/provide instruction on administration/in-clinic administration/evaluate administration
- AE assessment

Eligible subjects must have daily symptoms of DED for ≥ 6 months, a total score ≥ 40 on the SANDE questionnaire, history of artificial tear use in the 30 days prior to Screening, TBUT ≤ 6 seconds in both eyes, and anesthetized Schirmer's test tear volume ≥ 3 mm and <10 mm in both eyes.

If a subject complains of persistent dry eye symptoms after run-in medication is dispensed and between or during study subsequent visits, the site may provide the subject with unpreserved artificial tears (provided by the Sponsor), to be used only if necessary. The subject must return all used and unused artificial tears at each study visit so the site can conduct accountability to assess the use of artificial tears. Artificial tears may not be used

within 2 hours prior to any study visit; the subject may either be rescheduled or may wait at the site until 2 hours have passed since instillation if this occurs.

7.2. Treatment Period (Day 1 to Day 84 ± 4)

7.2.1. Visit 2 (Day 1/Confirmatory and Randomization Visit)

Procedures performed at Visit 2/Day 1 include:

- Concomitant medication review
- Urine pregnancy test (women of childbearing potential only)
- SANDE
- Individual symptom assessment (VAS)
- IP comfort assessment
- BCVA (logMAR)
- Biomicroscopy/external eye exam
- TBUT
- Corneal fluorescein staining
- Conjunctival lissamine green staining
- Anesthetized Schirmer's test
- Review inclusion/exclusion criteria
- Randomize eligible subjects
- Dispense IP/provide instruction on administration
- Dispense artificial tears (if needed)
- AE assessment
- Run-in medication accountability
- Artificial tear accountability, if applicable

7.2.2. Visit 3 (Day 7 ± 2)

Procedures performed at Visit 3/Day 7 ± 2 include:

- Concomitant medication review
- SANDE
- Individual symptom assessment (VAS)
- IP comfort assessment
- BCVA (logMAR)
- Biomicroscopy/external eye exam

- TBUT
- Corneal fluorescein staining
- Conjunctival lissamine green staining
- Dispense artificial tears (if needed)
- AE assessment
- Artificial tear accountability (if applicable)

7.2.3. Visit 4 (Day 14 ± 2)

Procedures performed at Visit 4/Day 14 ± 2 include:

- Concomitant medication review
- SANDE
- Individual symptom assessment (VAS)
- IP comfort assessment
- BCVA (logMAR)
- Biomicroscopy/external eye exam
- TBUT
- Corneal fluorescein staining
- Conjunctival lissamine green staining
- Dispense artificial tears (if needed)
- AE assessment
- Artificial tear accountability (if applicable)

7.2.4. Visit 5 (Day 28 ± 2)

Procedures performed at Visit 5/Day 28 ± 2 include:

- Concomitant medication review
- SANDE
- Individual symptom assessment (VAS)
- IP comfort assessment
- BCVA (logMAR)
- Biomicroscopy/external eye exam
- TBUT
- Corneal fluorescein staining
- Conjunctival lissamine green staining

- IOP measurement
- Dispense IP
- Dispense artificial tears (if needed)
- AE assessment
- IP accountability
- Artificial tear accountability (if applicable)

7.2.5. Visit 6 (Day 56 ± 4)

Procedures performed at Visit 6 include:

- Concomitant medication review
- SANDE
- Individual symptom assessment (VAS)
- IP comfort assessment
- BCVA (logMAR)
- Biomicroscopy/external eye exam
- TBUT
- Corneal fluorescein staining
- Conjunctival lissamine green staining
- Dispense IP
- Dispense artificial tears (if needed)
- AE assessment
- IP accountability
- Artificial tear accountability (if applicable)

7.3. Visit 7 (Day 84 ± 4) or Early Termination Procedures

At Visit 7/Day 84 ± 4 or the Early Termination Visit, all of the following end of treatment procedures must be completed:

- Concomitant medication review
- Urine pregnancy test (women of childbearing potential only)
- SANDE
- Individual symptom assessment (VAS)
- IP comfort assessment
- BCVA (logMAR)

- Biomicroscopy/external eye exam
- TBUT
- Corneal fluorescein staining
- Conjunctival lissamine green staining
- Anesthetized Schirmer's test
- IOP measurement
- Dilated fundus exam
- AE assessment
- IP accountability
- Artificial tear accountability (if applicable)

8. QUALITY CONTROL AND ASSURANCE

Silk Technologies and/or their contracted agents utilize standard operating procedures (SOPs) designed to ensure that research procedures and documentation are consistently conducted/prepared to the highest quality standards. These SOPs require compliance with FDA regulations and the International Council for Harmonisation (ICH) Good Clinical Practice (GCP) guidance.

The study will be monitored by CRAs/monitors to verify that the rights and well-being of human subjects are being protected, the reported data are accurate, complete, and verifiable, and that the conduct of the study is in compliance with the currently approved protocol, with ICH GCP, and with the applicable regulatory requirements.

To ensure compliance with GCP and all applicable regulatory requirements, Silk Technologies or its agent may conduct a quality assurance audit at any time during or after completion of a study. The Investigator will be given adequate notice if he/she is selected for an audit. The audit will include, but is not limited to: a review of all informed consent forms, medical records, and regulatory documentation; an assessment of study conduct and protocol compliance; and a review of the study materials receipt, storage, and administration. At the conclusion of an audit, the auditor will conduct a brief meeting with the Investigator to review the findings of the audit.

9. STATISTICS

9.1. General Considerations

This is a Phase 2, multicenter, randomized, double-masked, vehicle-controlled, dose-response, parallel group study to evaluate the ocular and systemic safety and efficacy of SDP-4 ophthalmic solution in subjects with moderate to severe DED.

Subjects with DED are planned to be randomized to 1 of 3 concentrations of SDP-4 (0.1%, 1.0%, or 3.0%) or vehicle in a 1:1:1:1 ratio, with 75 subjects randomized to each group.

A biostatistician will perform statistical analyses as agreed with the Sponsor according to the Statistical Analysis Plan (SAP).

All continuous study assessments will be summarized by treatment and visit (as applicable) using descriptive statistics (n, mean, median, standard deviation, minimum, and maximum). All categorical study assessments will be summarized by treatment and visit (as applicable) using frequency counts and percentages.

All study data will be listed by treatment, subject, and visit (as applicable).

The unit of analysis for efficacy will be the study eye.

Efficacy analysis will be conducted on the intent-to-treat (ITT) population (primary efficacy analysis) and the per protocol (PP) population (secondary efficacy analysis). Safety analyses will be performed using the safety analysis population. Definitions for the analysis populations may be found in Section 9.3.

9.2. Determination of Sample Size

A sample size of 70 subjects per treatment group will have 80% power to detect a treatment difference of 11.7 units in SANDE total score and 1.2 seconds in TBUT at Visit 7/Day 84 using a t-test with a 0.05 two-sided significance level. This calculation is based on the assumptions shown in Table 2. Note: TBUT is one of several secondary outcomes planned to be analyzed, but the sample size was derived using assumptions based on expected SANDE and TBUT values. Over-enrollment of 5 subjects per group/20 subjects per study is planned to account for discontinuations.

Table 2 Sample Sizes: Two-Group t-test of Equal Means

Assumptions	SANDE	TBUT
Test significance level, α	0.050	0.050
1 or 2 sided test	2	2
Difference in means, $\mu_1 - \mu_2$	11.684	1.192
Common standard deviation	24.500	2.500
Effect size, $\delta = \mu_1 - \mu_2 /\sigma$	0.477	0.477
Power (%)	80	80
n per group	70	70

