All continuous study assessments will be summarized by treatment and visit (as applicable) using descriptive statistics (n, mean, median, standard deviation, minimum, and maximum). All categorical study assessments will be summarized by treatment and visit (as applicable) using frequency counts and percentages.

All study data will be listed by treatment, subject, and visit (as applicable).

The unit of analysis for efficacy will be the study eye.

Sample Size Rationale

A sample size of 70 subjects per treatment group will have 80% power to detect a treatment difference of 11.7 units in SANDE total score and 1.2 seconds in TBUT at 12 weeks using a t-test with a 0.05 two-sided significance level. Over-enrollment of 5 subjects per group/20 subjects per study is planned to account for discontinuations.

Statistical Methods (continued):**Analysis Populations**

The intent-to-treat (ITT) population will include all randomized subjects who received IP.

The per protocol (PP) population is a subset of the ITT population, which will include all subjects who complete the study without major protocol deviations.

The safety population will include all subjects who received IP.

Approved

Table 1 Schedule of Visits and Examinations

	Visit 1 Day -14 ± 2 Screening	Visit 2 Day 1 Randomization	Visit 3 Day 7 ± 2 Treatment	Visit 4 Day 14 ± 2 Treatment	Visit 5 Day 28 ± 2 Treatment	Visit 6 Day 56 ± 4 Treatment	Visit 7 Day 84 ± 4 End of Treatment
Informed consent	X						
Review inclusion/exclusion criteria	X	X					
Demographics	X						
Medical and ocular history	X						
Concomitant medication/review	X	X	X	X	X	X	X
Urine pregnancy test	X	X					X
SANDE	X	X	X	X	X	X	X
VAS assessment of individual symptoms		X	X	X	X	X	X
IP comfort assessment		X	X	X	X	X	X
Best-corrected visual acuity	X	X	X	X	X	X	X
Biomicroscopy and external eye exam	X	X	X	X	X	X	X
Tear break-up time	X	X	X	X	X	X	X
Corneal fluorescein staining by zone	X	X	X	X	X	X	X
Conjunctival lissamine green staining by zone	X	X	X	X	X	X	X
Anesthetized Schirmer's test	X	X					X
Intraocular pressure measurement	X				X		X
Dilated fundus exam	X						X
Dispense run-in medication/instruction on run-in administration/evaluate administration	X						
Randomization		X					
Dispense investigational product (IP)/instruction on IP administration		X			X	X	
Dispense artificial tears ^a	X	X	X	X	X	X	

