9.5.3. Efficacy Analyses

The primary efficacy endpoint (SANDE) will be summarized using continuous summary statistics by treatment group and visit. The primary analysis will utilize a repeated measures mixed model where the dependent variable is the change from baseline score, treatment group is a fixed effect, baseline score is a covariate, and visit is a repeated measure on subject. The repeated measures mixed model is utilized to account for the effect of missing data under the assumption that the data are missing at random. Least squares means will be used to test each concentration of SDP-4 to vehicle. Sensitivity analyses for the primary endpoint will be performed using last observation carried forward (LOCF) as well as observed data only.

In order to minimize the impact of multiplicity in this dose-response study, the following hierarchy for analyses will be conducted (note: TBUT is one of several secondary outcomes planned to be analyzed, but the sample size was derived using assumptions based on expected SANDE and TBUT values):

1. Primary (SANDE) high concentration vs. vehicle
2. Primary (SANDE) middle concentration vs. vehicle
3. Primary (SANDE) low concentration vs. vehicle
4. Secondary (TBUT) high concentration vs. vehicle
5. Secondary (TBUT) middle concentration vs. vehicle
6. Secondary (TBUT) low concentration vs. vehicle

The comparisons will be conducted at $\alpha = 0.05$. Each comparison will be made in order until $P >$ (exceeds) 0.05. If $P \leq 0.05$, the comparison is statistically significant and testing is continued.

The planned analyses for all efficacy outcomes will be described in detail in the SAP, which will be finalized prior to database lock.

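### The 80% power stated for TBUT is for one stand-alone t-test; TBUT is reached only at step 4 of the test sequence, where power on the same basis is about 49–53%

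*Protocol*

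**What the plan says.** **Power statement.** Section 9.2 states that "70 subjects per treatment group will have 80% power to detect a treatment difference of 11.7 units in SANDE total score and 1.2 seconds" (the latter for TBUT, both at Day 84), by a two-sided t-test at 0.05. It notes that TBUT is a secondary outcome, but also that "the sample size was derived using assumptions based on expected SANDE and TBUT values". Table 2 gives TBUT its own column beside SANDE, each at 80% power with 70 per group. Five more per group are randomised to cover discontinuations, giving 75. The synopsis makes the same claim: 70 per group "will have 80% power to detect a treatment difference of 11.7 units in SANDE total score and 1.2 seconds in TBUT at 12 weeks".

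**Test sequence.** Section 9.5.3 orders six comparisons against vehicle: SANDE high, middle and low, then TBUT high, middle and low. Step 4 is "Secondary (TBUT) high concentration vs. vehicle". The rule is "Each comparison will be made in order until" P exceeds 0.05; at P of 0.05 or less, "the comparison is statistically significant and testing is continued".

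**Primary model.** The primary SANDE analysis is not a t-test but a mixed model in which "treatment group is a fixed effect, baseline score is a covariate, and visit is a repeated measure on subject".

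**The concern.** The power statement and the test sequence describe different things, and the protocol does not connect them. Section 9.2 treats TBUT as if it had its own test at 0.05. Section 9.5.3 gives it a formal test only after three SANDE successes. A fixed sequence cannot raise the chance of success at a later step: the probability of passing steps 1 to 4 is at most the probability of passing step 4 alone, and lower whenever a SANDE test can fail.

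TBUT is labelled secondary, but it is one of the two endpoints used to derive the sample size. A reader can fairly take the 80% as the chance of a formal TBUT result if the 1.2-second effect is real. That chance also depends on the SANDE effect of the lowest concentration, because a failure there stops formal testing of TBUT at the highest. Nothing in the power statement shows this dependence.

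**Working it through.** **Inputs from Table 2 and Section 9.5.3.** SANDE difference 11.684, SD 24.5; TBUT difference 1.192, SD 2.5; two-sided alpha 0.05; n = 70 per group (75 randomised); 1:1:1:1 allocation with one shared vehicle arm; the order and stopping rule above.

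**Assumptions, not in the protocol.** Within-subject SANDE–TBUT correlation ρ from 0 to 0.5; the effect at each concentration; the correlation r between the baseline covariate and the outcome.

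**Step 1: the plan's own figure.** Effect size d = difference / SD, with noncentrality d × √(n/2) on 2n − 2 = 138 degrees of freedom.

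- SANDE: d = 11.684 / 24.5 = 0.4769; 0.4769 × √35 = 2.82; power 80.0%.
- TBUT: d = 1.192 / 2.5 = 0.4768; power 80.0%.
- With 75 per group: 82.7% for both.

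Table 2 is therefore right for a single t-test.

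**Step 2: the sequence on the same t-test basis.** Simulation with 400,000 runs per scenario: bivariate normal SANDE and TBUT, three concentrations sharing one vehicle arm, pairwise t-tests, stop at the first P > 0.05, Table 2 effects at every concentration. Cumulative probability of passing each step, n = 70:

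| ρ | SANDE high | SANDE middle | SANDE low | TBUT high |
|---|---|---|---|---|
| 0 | 80.1% | 68.8% | 61.1% | 48.9% |
| 0.2 | 80.0% | 68.7% | 61.2% | 50.6% |
| 0.5 | 80.1% | 68.8% | 61.3% | 53.4% |

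Hand check at ρ = 0, where TBUT is independent of SANDE: 0.611 × 0.800 = 0.489. A separate multivariate normal calculation, with correlation 0.5 between contrasts because of the shared vehicle, gives 48.9% at ρ = 0 and 53.3% at ρ = 0.5. On this basis step 4 cannot exceed about 61%, the chance of winning all three SANDE tests, however high ρ is.

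With all 75 per group evaluable, TBUT high is 54.1% (ρ = 0) to 58.0% (ρ = 0.5).

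**Step 3: weaker SANDE effect at the low concentration (n = 70).**

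- At 75% of the planned effect, TBUT high is about 37–41%.
- At half the planned effect, the chance of three SANDE successes is 25.9%. TBUT high at ρ = 0 is then 0.259 × 0.800 = 20.7% (simulated 20.8%), rising to 23.3% at ρ = 0.5.

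**Step 4: allowing for a baseline covariate.** Suppose the Table 2 SDs are unadjusted and the covariate applies to both endpoints. The residual SD is then SD × √(1 − r²). For n = 70, with ranges over ρ = 0 to 0.5:

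| r | Single-test power | TBUT high in sequence | Same, half SANDE effect at low concentration |
|---|---|---|---|
| 0 | 80.0% | 48.9–53.4% | 20.8–23.3% |
| 0.3 | 83.6% | 55.8–59.7% | 23.9–26.3% |
| 0.4 | 86.4% | 61.8–65.0% | not run |
| 0.5 | 89.9% | 70.0–72.5% | 31.5–33.1% |

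At r = 0.58 the sequence figure is 78.2–79.8%, and at r = 0.6 it is 80.5–81.9%. A direct four-arm ANCOVA simulation (20,000 runs) agrees: 56.2–60.4% at r = 0.3 and 69.9–72.8% at r = 0.5. The repeated measures model itself was not simulated, because the protocol gives no visit correlations.

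**The case against.** Nothing in Section 9.2 is miscalculated. Table 2 is labelled a two-group t-test, shows its inputs, and nowhere claims to give power within the sequence. The secondary status of TBUT is noted beside the calculation and again in the sentence that introduces the hierarchy, so the order is open to any reader. Power per comparison is a usual basis for a first-in-human, phase 2 dose-response study. TBUT means and changes are reported at each visit whether or not the sequence reaches them. The 49–53% is also not the power of the planned analysis: it needs an assumed correlation, equal effects at all concentrations and no covariate gain. Across the scenarios the figure runs from about 21% to 82%.

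Much of this stands. The 80% is correct per comparison, a stopped sequence costs formal significance rather than data, and the size of the loss is conditional. It does not remove the point. The protocol chose to state 80% for TBUT and to size the trial partly on it, and neither note on the status of TBUT says the figure is before the sequence. The direction of the loss is certain under any single model. Sequence power reaches 80% only if r is about 0.58–0.60 (n = 70) and all three concentrations are equally effective on SANDE. Equal effects is a favourable case for this trial: the Introduction reports dose-dependent inhibition from 0.1% upward, and Section 3.2 places maximal NF-κB inhibition at 1%. A weaker effect at 0.1% is therefore plausible, although clinical effects by dose are unknown.

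**Conclusion.** The concern holds. The 80% for TBUT in Section 9.2 and the synopsis is the power of one isolated t-test, not of the formal test the protocol plans. On that same basis, with Table 2 effects at every concentration and ρ from 0 to 0.5, TBUT high has about 49–53% power at 70 per group, or 54–58% if all 75 are evaluable. With half the SANDE effect at the low concentration it is about 21–23% at 70 per group.

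These are not ceilings. A baseline covariate with r = 0.5 for both endpoints would give 70–73%, against 90% for the single test. The size therefore rests on inputs the protocol does not state; the direction does not. The stated power for SANDE high, the first test, is unaffected. The statement should be corrected, but the design need not change.

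**What to change.** In Section 9.2 and in the synopsis sample size rationale, say that the 80% is for each single concentration-versus-vehicle t-test before the Section 9.5.3 sequence. Add the power for TBUT high within the sequence, with its assumptions: test model, SANDE–TBUT correlation, effect at each concentration, and whether a covariate gain is included. For example:

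> The 80% applies to each single concentration-versus-vehicle t-test before the sequence in Section 9.5.3. On the same t-test basis, with 70 per group, all concentrations at the Table 2 differences and an assumed SANDE–TBUT correlation of 0 to 0.5, power for TBUT at the high concentration within the sequence is about 49–53%. Any gain from the baseline covariate is not included.

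The sponsor should substitute its own assumptions where it has them.

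The cost is wording in two places. No subjects are added, and sample size, alpha, test order and analysis stay as they are. The drawback is a less favourable TBUT figure and the need to commit to assumptions the protocol now leaves unstated.
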